12. ADMINISTRATION

12.1. Regulatory and Ethical Considerations

This addendum protocol and its accompanying informed consent, along with the main study, will be submitted to the HREC for review and approval.

12.2. Informed Consent

A written informed consent is required for each patient before any study-related activities are performed.

12.3. Confidentiality

Subject privacy and confidentiality will be protected in accordance with the main protocol (Section 14.3)

12.4. Study Conduct and Management

The general study conduct, including quality control and quality assurance, data handling and record retention, and investigational device management, will be performed in accordance with the main protocol.

APPENDIX 5. CONTINUED FOLLOW-UP PROTOCOL ADDENDUM

Appendix 5. REGENT-1 Study Continued Follow-up Addendum

1. INTRODUCTION

The REGENT-1 study was designed to assess the technical feasibility and safety of the ReCET therapy in participants inadequately controlled on non-insulin glucose-lowering medications (NIS Cohort) and on insulin (IS Cohort). Following the enrollment of initial 30 participants, a second generation catheter (Gen 2) was introduced to accommodate a broader range of duodenal diameters and improve the circumferential coverage of the treatment.

Participants were followed for 48 weeks post procedure in the main protocol. This addendum describes the plan for continued follow-up after 48 weeks.

2. OBJECTIVES AND ENDPOINTS

The primary objective of continued follow up beyond one year is to enable data collection for assessment of treatment durability.

A secondary objective is to assess the safety and outcomes of repeat treatment with the ReCET procedure in participants that meet criteria for repeat treatment.

Objectives	Endpoints
Durability and Clinical Outcomes 
• To assess the durability of the ReCET therapy beyond one year• To assess the effectiveness of the re-treatment with ReCET therapy	
• Change in HbA1c from baseline by visit after the initial ReCET procedure• Change in HbA1c by visit after re-treatment with the ReCET procedure• Change in weight by visit• Proportion of patients with an HbA1c $\leq 7.0\%$ by visit• Change in background medication use
Safety 
• To assess the safety of re-treatment with the ReCET procedure	
• Incidence of device- and/or procedure-related Serious adverse events after a repeat ReCET procedure at 3 month of the procedure

3. CONTINUED FOLLOW UP

3.1. Patient Population for Continued Follow-up

Study participants meeting the criteria below will be followed for 2 years:

- In NIS Cohort
- Treated with the Gen 2 catheter
- Has completed 48 weeks follow up
- Consented to be followed for an additional year

3.2. Follow Up Schedule

Participants will be followed according to the Schedule of Activities listed in **Table 1** below. Onsite visits will be performed every 6 months and remote visits will be performed every 3 months in between onsite visits.

Participants should be managed per standard of care to achieve optimal glycemic control. Participants not achieving glycemic control target may be evaluated for re-treatment with the ReCET therapy as described in **Section 4** below.

Table 1. Schedule of ACTIVITIES in the Second Year

	Remote Visits	In Clinic Visits	Exit
Time points (months)	15, 21	18, 24	
Visit window (days)	±14	±14	
SUBJECT RELATED INFO/ASSESSMENTS			
Medical history changes		X	X
Concomitant medication	X	X	X
Lifestyle Counseling	X	X	X
Hypoglycemic episodes	X	X	X
Adverse events	X	X	X
Exit			X
VITAL SIGNS AND PHYSICAL EXAMINATION			
Body weight, BMI		X	X
Blood pressure and pulse rate		X	X
LABORATORY TESTINGS			
Fasting plasma glucose		X	X
HbA1c		X	X

4. RE-TREATMENT WITH THE RECET THERAPY

Participants can be assessed for re-treatment eligibility throughout the duration of the follow up. Participant will be assessed for response to the initial ReCET therapy to determine if continued follow-up or re-treat is warranted. When considering re-treatment, the investigator should evaluate any changes in a participant's medical conditions and assess whether ReCET procedure is still appropriate for the participant. Currently, no data exists on the safety and efficacy of re-treatment with the ReCET procedure. The investigator should discuss the re-treatment in the context of other treatment options with the participant and obtain Informed Consent prior to the procedure.

4.1. Re-treatment Eligibility

Participants meeting the following criteria may be considered for re-treatment with the ReCET procedure:

- In NIS Cohort
- Treated with the Gen 2 catheter
- Has completed 48 weeks follow up
- Is sub-optimally controlled, defined as HbA1c $\geq 7.5\%$

- Had responded to the initial ReCET therapy, defined as HbA1c reduction of $\geq 1.0\%$ at any time after the initial ReCET procedure
- Consented to re-treatment and be followed up for at least one year after the re-treatment

In addition, the participant should **not have any of the exclusion criteria** listed in the main protocol with the exception of exclusion criteria # 4 and #5 (**Section 5.2 of the main protocol**).

4.2. Re-treatment Procedure and Periprocedural Patient Care

ReCET procedure for re-treatment and per-procedural participant management should follow the same guidelines provided in **Section 6** of the main protocol.

Participants will be instructed on transitional diet, the importance of hydration, use of CGM for 4 weeks post procedure, and be educated on monitoring hypoglycemic events as described in the main protocol.

4.3. Evaluations and Follow-up Assessments after Re-Treatment

Participant evaluation and follow-up assessments after re-treatment is listed in **Table 2**.

4.3.1. Assessment before Re-treatment

Before re-treatment with the ReCET procedure, the following evaluations/procedures should be performed:

- Informed Consent for re-treatment
- Participant eligibility
- Weight, BMI
- Vital signs
- Any changes in medical history
- Concomitant medications including diabetes medication review
- Laboratory tests:
 - Hematology (CBC with differentials)
 - Metabolic panel
 - Glycemic parameters (HbA1c, FPG)
- CGM
- Pregnancy test for females capable of becoming pregnant

4.3.2. ReCET Procedure

The ReCET procedure and periprocedural patient management follows **Section 6** of the main protocol.

The following assessments/procedures will be performed at this visit.

- Endoscopic exclusion criteria and procedural data
- Vital signs prior to discharge
- Concomitant medications
- Assessment of AEs
- Diabetes review and medication titration by treating physician
- Initiate CGM prior to discharge

4.3.3. Follow Up Visits

After re-treatment with ReCET procedure, participants should be managed according to the guidelines described in the main protocol. Participants should be followed according to the Scheule of Activities listed in **Table 2**.

Onsite visits should be performed at 1, 3 and 6 months and every 6 months thereafter. The following data will be collected during the onsite visits:

- HbA1c, FPG
- Weight, BMI
- Vital signs
- Adverse events or any change in medical conditions
- Concomitant medications
- Lifestyle counseling
- CGM

CGM data will be collected for the first 4 weeks after the procedure and at 3, 6, and 12 months after retreatment. Endoscopic follow up should be performed at 1 month after the procedure.

Remote visits should be performed every 3 months in between onsite visits. The goal of the remote visits is to monitor patient's blood glucose levels, provide diabetes self-management counseling, and make medication changes if necessary.

For remote visits, the following data will be collected:

- Adverse events or any changes in medical conditions
- Concomitant medications
- Lifestyle counseling

5. SAFETY ASSESSMENT

Refer to Section 9 of the main protocol for safety assessment.

6. MEDICAL SAFETY MONITORING

Refer to Section 10 of the main protocol for medical monitoring.

7. STATISTICAL DESIGN AND ANALYSIS

Refer to Section 11 of the main protocol for statistical analysis.

8. ADMINISTRATION

8.1. Regulatory and Ethical Considerations

This addendum protocol and its accompanying informed consent, along with the main study protocol, will be submitted to the HREC for review and approval.

8.2. Informed Consent

Participants must consent to be followed beyond 48 weeks by providing a written informed consent. Additionally, written informed consent is required for re-treatment with the ReCET therapy before the procedure.

8.3. Confidentiality

Subject privacy and confidentiality will be protected in accordance with the main protocol (Section 14.3)

8.4. Study Conduct and Management

The general study conduct, including quality control and quality assurance, data handling and record retention, and investigational device management, will be performed in accordance with the main protocol.

Table 2. Schedule of Activities Before and After Re-treatment

	Before Re-Treatment	Repeat ReCET Procedure	Week 1	Week 2	Month 1	Month 3	Month 6	Month 9	Month 12/Exit
Clinic Visit(V)/Remote Visit (R)	V	V	R	R	V	V	V	R	V17
Visit window (days)	-28 to -1	0	±2	±3	±5	±7	±14	±14	±14
SUBJECT RELATED INFO/ASSESSMENTS									
Informed consent for Re-treatment	X								
Eligibility for re-treatment	X								
Medical history changes									X
Concomitant medication	X	X	X	X	X	X	X	X	X
Lifestyle Counseling	X		X	X	X	X	X	X	X
CGM use	X		X	X	X	X	X		X
Exit									X
VITAL SIGNS AND PHYSICAL EXAMINATION									
Body weight, BMI	X				X	X	X		X
Blood pressure and pulse rate	X	X			X	X	X		X
LABORATORY TESTINGS									
Fasting plasma glucose	X				X	X	X		X
HbA1c	X				X	X	X		X
Metabolic Panel ^[1]	X								
CBC with differential	X								
Pregnancy test ^[2]	X								
ENDOSCOPIES									
ReCET procedure		X							
EGD follow up					X				
SAFETY									
Hypoglycaemic episodes	X	X	X	X	X	X	X	X	X
Adverse events	X	X	X	X	X	X	X	X	X

^[1] Metabolic panel includes albumin, total protein, , ALP (alkaline phosphatase), ALT (alanine transaminase), AST (aspartate aminotransferase), bilirubin, urea, creatinine, eGFR.

^[2] For women with child-bearing potential.

1. LIST OF ABBREVIATIONS AND DEFINITIONS

Abbreviation	Abbreviated Defined
AACE	American Association of Clinical Endocrinologists
ADA	American Diabetes Association
AAE	Anticipated Adverse Event
ADE	Adverse Device Effect
AE	Adverse Event
AESIs	Adverse Events of Special Interest
ALP	Alkaline Phosphatase
ALT	Alanine Aminotransferase
ASADE	Anticipated Serious Adverse Device Effect
AST	Aspartate Aminotransferase
BMI	Body Mass Index
BUN	Blood Urea Nitrogen
CEC	Clinical Events Committee
CFR	Code of Federal Regulations
CGM	Continuous Glucose Monitoring
COVID-19	Coronavirus Disease 2019
CRF	Case Report Form
CSR	Clinical Study Report
Diabetes Site	The site where the Investigator performs study follow up visits and diabetes management.
DMR	duodenal mucosal resurfacing
DSMB	Data Safety and Monitoring Board
DTSQ	Diabetes Treatment Satisfaction Questionnaire
EKG	Electrocardiogram
eGFR	Estimated Glomerular Filtration Rate eGFR calculated by Chronic Kidney Disease Epidemiology Collaboration (CKD-EPI) Equation (2021)
Endoscopy Site	The site where the Index Procedure is performed.
FPG	Fasting Plasma Glucose
GCP	Good Clinical Practice
GI	Gastrointestinal
GLMs	Glucose Lowering Medications
HbA1c	Glycosylated Hemoglobin
HDL	High-Density Lipoprotein
HOMA-IR	Homeostatic Model Assessment of Insulin Resistance
HIPAA	Health Insurance Portability and Accountability Act
ICF	Informed Consent Form
ICH	International Conference for Harmonization
IDE	Investigational Device Exemption

Abbreviation	Abbreviated Defined
I/E	Inclusion/Exclusion Criteria
IP	Investigational Plan
IRB	Institutional Review Board
ISO	International Organization for Standardization
ITT	Intent-to-Treat
LDL	Low-Density Lipoprotein
MedDRA	Medical Dictionary for Regulatory Activities
PP	Per Protocol
SAE	Serious Adverse Event
SAP	Statistical Analysis Plan
SU	Sulfonylurea
T2D	Type 2 Diabetes Mellitus
% TBWL	% Total Body Weight Loss
TIR	Time in range
UADE	Unanticipated Adverse Device Effect
ULN	Upper Limit of Normal

2. REVISION HISTORY

Version 1.0 of the Statistical Analysis Plan is the initial version of this document that has been released for production.

3. INTRODUCTION

This statistical analysis plan (SAP) describes the planned statistical methods to be used during the reporting and analysis of data collected under the Clinical Investigation Protocol entitled *Safety and Feasibility of Endoscopic Application of a Novel Therapy for Duodenal Mucosal Regeneration in the Treatment of Type II Diabetes (REGENT-1-US Study)*, Doc. No. 346. This SAP should be read in conjunction with the study protocol and case report forms (CRFs).

The REGENT-1-US study is a multicenter, open-label, treatment-only study conducted in Australia. The study is designed to assess the feasibility and preliminary safety of the Endogenex device for endoscopic duodenal cellular regeneration in patients with type 2 diabetes (T2D) inadequately controlled on glucose-lowering medications. The protocol enrolled patients who were treated with non-insulin glucose-lowering agents; a tabulation of the treatment and number of patients is presented below.

Device Generation 1 / 600 Volts / Single Treatment (n)	Device Generation 1 / 600 Volts / Double Treatment (n)	Device Generation 2 / 750 Volts / Double Treatment (n)	All Patients (n)
3	7	10	20

This plan is developed for analysis and reporting of the 48-week follow up data. The SAP may be revised in the future to address additional follow up data analysis beyond 48 weeks, if necessary.

Patients are considered enrolled in the study once the patient has passed endoscopic screening and proceeded to the Index procedure. **Screen failures** are defined as patients who consented to participate in the clinical study and started the screening tests specified by the protocol but are not subsequently enrolled into the study. Procedure success was defined as at least 6cm of duodenum was successfully treated.

The following analysis populations are defined for the presentation of the results from this study: *Intent-to-Treat* (ITT), *Full Analysis Set* (FAS) [referred to in the study protocol as the modified Intent-to-Treat (mITT) population], *Per-Protocol* (PP) and *Completed Cases* (CC). (Ref. Section 11.3 of the study protocol).

The primary and secondary safety analyses will be performed using the ITT population. The primary effectiveness analyses will be performed using the FAS population. The Per-Protocol population and Completed-Cases population will be used for the sensitivity analyses of the primary and secondary effectiveness endpoints.

Intent-to-Treat: The Intent-to-Treat population includes all enrolled patients, regardless of the patient having received the target treatment (at least 6cm of duodenum treated). The point of enrollment occurs when a patient has provided written informed consent and an energy delivery has been attempted during the index procedure.

Full Analysis Set: The FAS population consists of the ITT population patients who received the target treatment (at least 6 cm of duodenum treatment) and that have at least one post-treatment follow-up examination.

Per-Protocol: The Per-Protocol population is a subset of the FAS population and includes all patients who received the target treatment, do not have any major eligibility violations, and maintained stable glucose-lowering medications for 24 weeks post-procedure. The definition of what constitutes a major eligibility violations will be established before the study database is locked.

Completed Cases: The Completed Cases population is a subset of the Per-Protocol population and includes all patients who received the target treatment, do not have any major eligibility violations, and maintained stable glucose-lowering medications for 24 weeks post-procedure, and completed the final Week 48 End of Study Visit.

The details contained in this plan include the source code for the assessment of poolability across a myriad of factors and the analysis of each of the endpoints. Additionally, the structure of the table designs and a comprehensive index of the tables and listings has been provided.

This document contains information to support the generation of a Clinical Study Report (CSR). The planned analyses identified in this SAP may be included in regulatory submissions, medical presentations, and manuscripts. Exploratory analyses, not identified in this SAP, may be performed to support the clinical development program. Any post-hoc or unplanned analyses that are performed, but not identified in this SAP, will be clearly identified in the final report of the results. The structure and content of this SAP are designed to meet the requirements identified by the FDA and the International Conference on Harmonization (ICH) Guidance on Statistical Principles for Clinical Trials.

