Safety and Feasibility of Endoscopic Application of a Novel Therapy for Duodenal Mucosal Regeneration in the Treatment of Type II Diabetes (**REGENT-1 Study**)

Protocol number: **196**

Principal Investigator:

[name].
The Bariatric & Metabolic Institute
The BMI Clinic
[name]
[name]
[name]
Australia

Local Sponsor:

DyaMX Australia Pty Ltd
C/- Case Governance Pty Ltd
[name]
[name]
[name]
[REDACTED]

Medical Monitor

[name]
Division of Gastroenterology
Department of Internal Medicine
[name]
Baylor University Medical Center
[name], USA
[REDACTED]

Version O

30 Sep 2023

PREAMBLE

The REGENT-1 study is designed to assess the feasibility and preliminary safety of the Endogenex device for endoscopic duodenal mucosal regeneration in patients with type 2 diabetes (T2D) inadequately controlled on glucose-lowering medications. The protocol initially enrolled participants who were treated with non-insulin glucose-lowering agents. Following the enrollment of an initial group of participants supporting the safety and feasibility of the procedure, a second cohort is added to the study to assess the treatment in patients treated with basal insulin (referred as insulin cohort, IS cohort).

Insulin cohort participants will be treated with the same investigational device and procedure and be followed up according to the same follow-up schedule as described in the original protocol. For simplicity and clarity, the background medication management and their associated modifications to the inclusion/exclusion criteria, along with other necessary modifications in IS cohort are described in a protocol addendum (**Appendix 4**). The original protocol (#196), also referred as the “main protocol”, is kept unchanged. Participants enrolled under the main protocol will be referred as non-insulin (NIS) Cohort in study analysis and reports.

A second addendum to the protocol is added to enable longitudinal follow up of the participants beyond one year and the possibility of repeat treatment if clinically justified (**Appendix 5**).

TABLE OF CONTENTS

PREAMBLE	2
LIST OF ABBREVIATIONS	7
PROTOCOL SUMMARY	9
1 BACKGROUND	15
1.1 Type 2 Diabetes	15
1.2 Duodenal Mucosal Resurfacing	15
2 DEVICE DESCRIPTION	16
2.1 System Description	16
2.1.1 Generator and Controller	17
2.1.2 Catheter	18
2.1.3 Connecting Cables and Switchbox	20
2.2 Proposed Mechanism of Action	20
2.3 Proposed Indication	21

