4 STUDY DESIGN

4.1 Study Design

This is a multicenter, single-arm, open-label study conducted in Australia. The study enrolls participants inadequately controlled on non-insulin medications (NIS Cohort) and on basal insulin (IS Cohort). The NIS Cohort is described below. The IS Cohort is described in **Appendix 4**.

Twenty (20) participants will be enrolled initially and up to 60 participants may be enrolled in NIS Cohort. The first 30 participants will be treated with the first-generation catheter (Gen 1) and the next 20-30 participants will be treated with the second-generation device (Gen 2). Patients who sign the informed consent and are deemed eligible following a general and endoscopic screening will be enrolled in the study.

Participants with T2D inadequately controlled on 1-4 non-insulin glucose-lowering medication(s) will be screened for study eligibility. Eligible participants who consent to participate in the study will maintain his/her background glucose-lowering medication(s) stable (no medication or dose change) for at least 12 weeks prior to baseline visit.

The index procedure will be performed under general anesthesia or deep sedation and within 28 days from the baseline visit. Participants will undergo endoscopic screening immediately prior to the DMR procedure, and eligible participants will undergo the DMR procedure. Participants may be discharged per local hospital's guideline; an overnight stay is not required but allowed per local policy and investigator's clinical judgement. A participant is enrolled in the study when an energy delivery is attempted. Participants excluded during endoscopic screening will be considered a screen failure and will be followed for 30 days after the procedure for safety.

Post index procedure, participant will be on a transitional diet consisting of clear liquids for 24 hours followed by full liquid diet for 3 days, pureed food for 3 days, and soft food for one week.

Background medication will be titrated to the pre-procedure dose and maintained for 24 weeks post index procedure and the transitional diet period per Section 6.2. After the 24-week follow-up visit, participants will be managed according to the current (2020) guidelines of the American Diabetes Association² and their glucose-lowering medications will be optimized to achieve individualized A1c goals, which for most individuals is a target of less than 7.0%.

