4. STUDY DESIGN

The IS Cohort will enroll 20 participants initially and up to 30 participants with T2D on basal insulin therapy. Patients who sign the informed consent and are deemed eligible following a general and endoscopic screening will be enrolled in the study.

The index procedure and periprocedural care is described in the main protocol.

The background glucose-lowering medications at baseline and during follow up for each cohort are shown in **Figure 1**.

Eligible participants will be on long-acting insulin with or without short- or rapid acting insulin (up to 60 IU/day and no more than 30% of short/rapid acting components) with or without up to four stable dose of non-insulin glucose lowering medications for at least 3 weeks at baseline.

Post procedure, non-insulin background medications will be resumed to the baseline dose and maintained during the follow-up phase. Insulin dose will be titrated based on fasting glucose levels and may be discontinued if the daily insulin dose is reduced to 10 IU or 0.1 IU/kg and fasting glucose level is at target.

Participants will receive lifestyle-modification counseling sessions at scheduled intervals to promote adherence to a diet and lifestyle suitable for individuals with diabetes. Counseling will be provided by a member of the research team (endocrinologist, dietitian, nurse, etc.) trained in the delivery of lifestyle counseling for diabetes.

Participants will undergo the same follow up schedule, study procedures and data collection as those described in the main study protocol.

[figure not shown]

Figure 1. Insulin Cohort Design

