11. STATISTICAL DESIGN AND ANALYSIS

Statistical analysis will be performed in accordance with the main protocol. The data on safety and procedural feasibility will be analyzed for each cohort and overall. The data on efficacy endpoints will be analyzed by treatment cohort.

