5. STUDY OVERVIEW

5.1. Study Design and Description of the Study Device

This is a multicenter, open-label, treatment-only study conducted in the United States. A total of 20 participants is planned for the study. The study will test two treatment parameters. The first 10 participants will be treated at a generator setting of 600 Volts/13 bursts/350 KHz (600V) and the second group of 10 participants at 750 Volts/8 bursts/350KHz (750V). In the 600V group, the first 5 participants will be enrolled/treated with the investigational device sequentially with at least 14 days observation time between each procedure. In the 750V group, the first participants will be enrolled/treated with the investigational device sequentially with at least 6 days observation time between each procedure.

Participants with T2D inadequately controlled on 2-3 non-insulin glucose-lowering medication(s) will be screened for study eligibility. Eligible participants who consent to participate in the study will maintain his/her background glucose-lowering medication(s) stable (no medication or dose change) for at least 12 weeks prior to baseline visit.

The index procedure will be performed under general anesthesia or deep sedation and within 21 days from the baseline visit. Participants will undergo endoscopic screening immediately prior to the DMR procedure, and eligible participants will undergo the DMR procedure. Participants may be discharged per local hospital's guideline; an overnight stay is not required but allowed per local policy and investigator's clinical judgement. A participant is enrolled in the study when the Endogenex catheter insertion is attempted. Participants excluded during endoscopic screening will be considered a screen failure and will be followed for four weeks after the procedure for safety.

Post index procedure, participants will be on a transitional diet consisting of clear liquids for 24 hours followed by a full liquid diet for 3 days, pureed food for 3 days, and soft food for one week, and then return to normal food as tolerated.

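### The SAP supplied with protocol 196 names another study (REGENT-1-US, Doc. No. 346), leaves unclear whose data it covers, and has no insulin-cohort population, column or insulin endpoint

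*SAP*

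**What the plan says.** **Identity.** The protocol's title page gives "Protocol number: 196", and its section 4.1 places REGENT-1 in Australia. SAP section 3 says that it analyses data collected under "REGENT-1-US Study)*, Doc. No. 346".

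**Country.** SAP section 3: "The REGENT-1-US study is a multicenter, open-label, treatment-only study conducted in Australia". SAP section 5.1: "This is a multicenter, open-label, treatment-only study conducted in the United States".

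**Participants.** Protocol section 4.1 allows up to 60 in the non-insulin (NIS) cohort, starting with 20: "The first 30 participants will be treated with the first-generation catheter (Gen 1) and the next 20-30 participants will be treated" with the second-generation device. Section 5 gives 50-60, and section 11.2 gives 20 to 30. For the insulin (IS) cohort, Appendix 4 section 4 says "The IS Cohort will enroll 20 participants initially and up to 30 participants with T2D on basal insulin therapy". SAP section 3 tabulates 20 patients in three groups of 3, 7 and 10 by device generation, voltage and single or double treatment. It describes those enrolled as treated with non-insulin agents.

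**Cohort analysis.** Appendix 4 section 11 asks for safety and procedural feasibility in each cohort and overall. On efficacy it says "The data on efficacy endpoints will be analyzed by treatment cohort". Appendix 4 Table 1 also lists an insulin outcome at 24 weeks, maintained at 48 weeks (its wording is broken in the text available).

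**The concern.** A SAP has to tell a programmer whose data enter the tables. This one names a different study number and title, gives two countries, and lists a number of patients that does not match the protocol beside it.

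If it does govern protocol 196, the cohort structure added by Appendix 4 is missing from the displays. The insulin endpoint would have no analysis definition, and the by-cohort tables would have to be designed without a plan, possibly after the data are seen.

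The denominator of the primary safety endpoint is also at stake, because 20 patients and 70-90 patients support very different statements about related serious adverse events.

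**Working it through.** **1. The SAP's own figure.** 3 + 7 + 10 = 20. This agrees with the 20 in SAP sections 5.1 and 5.3, so the number is internally consistent.

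**2. The two documents side by side.**

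| Item | Protocol 196 | SAP |
|---|---|---|
| Study | REGENT-1, No. 196 | REGENT-1-US, Doc. No. 346 (section 3) |
| Country | Australia | Australia (3); United States (5.1) |
| Participants | NIS 50-60 (4.1, 5), but 20-30 (11.2); IS 20-30 (App. 4) | 20, non-insulin |
| Background drugs (NIS) | 1-4 | 2-3 (5.1) |
| Baseline to procedure | within 28 days | within 21 days (5.1); -28 to -1 days (8.6) |
| First participant | Q2 2021 | Q4 2021 (5.4) |
| Point of enrolment | energy delivery attempted (5.3) | catheter insertion attempted (5.1); energy delivery attempted (3, 6) |
| HbA1c responder | 0.3% or more (3) | mainly 0.5% or more (4.2.1, 9); 0.3 in Table 14.4.4 |

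The SAP's conflicts on country, baseline window, point of enrolment and responder threshold are internal to it. They stand whichever protocol it serves. The other differences are errors only if it serves protocol 196; they may match protocol 346, which is not available.

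**3. Share outside the stated 20, if the SAP serves protocol 196.** Share = (N - 20) / N, supposing that all 20 belong to protocol 196.

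- Sections 4.1 and 5 plus Appendix 4: N = 50 + 20 = 70 to 60 + 30 = 90. Outside: 50/70 = 71.4% to 70/90 = 77.8%.
- NIS alone, sections 4.1 and 5: 30/50 = 60.0% to 40/60 = 66.7%.
- Section 11.2's 20-30 as the NIS number, plus IS: 20/40 = 50.0% to 40/60 = 66.7%.
- Section 11.2 alone: 0/20 = 0% to 10/30 = 33.3%.

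The last two lines look out of date. Appendix 4 section 1 reports 27 patients already treated, and Appendix 5 section 1 says that the Gen 2 catheter came in after the first 30. If the SAP serves only protocol 346, the share outside is 100%.

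**4. What the denominator does to the primary endpoint.** Suppose, for illustration, no related serious adverse events. The exact two-sided 95% upper limit is 1 - 0.025^(1/n):

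- n = 20: 16.8%
- n = 50: 7.1%
- n = 70: 5.1%
- n = 90: 4.0%

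**5. The insulin cohort in the SAP.** The Level 1-3 displays (section 7) have columns by device generation, voltage and treatment, plus all patients; none is for IS. None of the 18 secondary endpoints in section 4.2.1 concerns coming off insulin. The only trace is an 'IS population' named in section 10.1.3 for Tables 14.3.4a, 14.3.5a and 14.3.5.1a and defined nowhere.

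**6. Which study is it?** For an adapted document: it cites protocol sections 3 and 11.3 and Appendix 2, its ITT, FAS and PP wording tracks protocol section 11.3, and most of its protocol visit windows match. For another study's document: the study name, document number, 20 patients and voltage groups. Section 7.2 mentions five comparison sets where section 7 defines two, and section 10.1.1 mentions two randomized groups in a study without randomization. These suggest reused text but do not show its source. The SAP is Version 1.0, so none of this is a record of superseded text.

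**The case against.** The best defence is that little is lost. Protocol 196 is descriptive. Section 11.4 tests no hypothesis and specifies the summary statistics, and Appendix 4 section 11 already prespecifies analysis by cohort. SAP section 3 requires unplanned analyses to be labelled. This stands as a limit on the harm: no test or decision rule is compromised. It does not supply the missing definition of the insulin endpoint or the cohort displays, and it does not say whose data the SAP covers.

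Several stronger readings are tempting, and the documents do not support them:

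- *The SAP is certainly another study's.* The evidence in step 6 of the check points both ways.
- *71-78% of participants are outside, without condition.* That needs the SAP to serve protocol 196 and sections 4.1 and 5 to prevail over 11.2.
- *The insulin cohort has no endpoints.* Appendix 4 Table 1 appears to share most endpoints between cohorts: related serious adverse events, procedure success and time, HbA1c, FPG, HOMA-IR, meal-test measures, medication use, liver enzymes, blood pressure, lipids and weight. The SAP covers all of these. Only the insulin-specific endpoint and the split by cohort are missing.
- *Every table and population is tied to the 20.* The ITT, FAS and PP definitions carry no number, and every display has an all-patients column.
- *Required results by catheter generation are left unplanned.* No protocol section requires them, and the SAP's Comparison Set 1 already separates the generations.
- *The two studies' patients will be pooled.* Nothing in either document says so.

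One caution on carrying definitions over: the PP rule of stable glucose-lowering medication for 24 weeks needs interpreting for a cohort whose insulin is titrated under Appendix 4.

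**Conclusion.** The point holds and needs correcting before the SAP is used. As written, the SAP does not identify the study or the participants that it covers, and it cannot deliver the by-cohort analysis that Appendix 4 section 11 requires.

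The size depends on a fact that the documents do not give. If the SAP serves protocol 346, protocol 196 has no SAP here. If it serves protocol 196, 50-70 of 70-90 planned participants are outside its stated 20, on the numbers in sections 4.1 and 5 and Appendix 4. Section 11.2 would make that share smaller and is itself in conflict. In both cases all 20-30 IS participants lack a population definition, a column and their insulin-specific endpoint.

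The shared endpoints and the ITT, FAS and PP wording are usable, so this is a repair and not a rewrite.

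**What to change.** In SAP section 3, state the governing protocol number and version, the country, and exactly which participants are covered.

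- **If the SAP is for protocol 346:** issue a separate SAP for protocol 196.
- **If it is for protocol 196:** correct the participant table. Add NIS, IS and overall displays for safety and feasibility, and by-cohort displays for efficacy. Add the Appendix 4 insulin endpoint, and define or remove the IS population. Then reconcile with the protocol the number of background drugs, the baseline window, the first-enrolment date, the point of enrolment and the HbA1c responder threshold. Columns by catheter generation are optional.

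Protocol section 11.2 should be reconciled with sections 4.1 and 5, or a corrected SAP will inherit the conflict.

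The cost is a SAP revision plus the reconciliation of section 11.2, with no new data. The SAP speaks of database lock as still ahead, but the documents do not show whether it has since happened. The revision should precede lock if it has not.
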